Appendix II. Patient Activation, Self-Reported Outcomes of Care, and Patient Experience
 (Number of questions = 65)

Measure	Item Count	Example Content	Internal Consistency Reliability	Why Selected (Why alternatives were not?)
		
 How would you rate the coordination of your care between these nurses and other providers and your doctor? Thinking about these nurses or other providers in your doctor's office, how would you rate their knowledge of you as a person, including values and beliefs that are important to you? 		items related to care team coordination and these questions have similar content as the ACES items ([name], et al, 2007). ⁹⁰
Ability to Participate in Social Roles and Activities (PROMIS Short Form 8a)	8	
 I have trouble doing all of the family activities that I want to do I have to limit my regular activities with friends. I have trouble doing all of the work that is really important to me (include work and home) 	0.85-0.94	The PROMIS social role subscale was selected because the composite covers a health domain central to patient activation and engagement. Further, the measure was developed through extensive item preparation and review, EFA-, CFA- and IRT-guided item banks help provide increased measurement precision and flexibility. ⁹¹
Patient Health Questionnaire (PHQ-4) Depression and Anxiety	4	
Over the past 2 weeks, how often have you been bothered by these problems:
 
 Feeling nervous, anxious or on edge Not being able to stop or control worrying Feeling down, depressed, or hopeless Little interest or pleasure in doing things 	0.82	Compared to the PROMIS measures of anxiety and depression, the PHQ-4 is parsimonious, is used more extensively in primary care settings for quality improvement and research purposes. While the PROMIS measures are longer and cover a broader range of symptoms, research has not demonstrated the relative advantage of the PROMIS measures compared to the PHQ-9 or PHQ-4 for use in primary care settings. ⁹²

PRINCIPAL INVESTIGATOR (LAST, FIRST, MIDDLE): [name]

Appendix II. Patient Activation, Self-Reported Outcomes of Care, and Patient Experience
 (Number of questions = 65)

Measure	Item Count	Example Content	Internal Consistency Reliability	Why Selected (Why alternatives were not?)
Physical Function (PROMIS Short Form 12a)	13	
 • Are you able to do yard work like raking leaves, weeding, or pushing a lawn mower? • Are you able to bend down and pick up clothing from the floor? • Are you able to push open a heavy door? 	0.86-0.95	Research indicates that the PROMIS physical function composite, which is comprised of item response theory-based items, can result in greater responsiveness and precision across a broader range of physical function compared to other physical function measures. This can reduce sample size requirements and thus study costs. ⁹³
Demographics	11	Age, gender, race, ethnicity, self-rated English literacy, preferred language, interpreter use, employment status, marital status, education, and military status		Census specifications will be used, when applicable.

PRINCIPAL INVESTIGATOR (LAST, FIRST, MIDDLE): [name]

Appendix III. Primary Care Teamwork, Relational Coordination, Leadership, and Culture Survey

(Number of questions= 40 excluding the team composition question)

Measure	Level	Item Count	Example Content	Internal Consistency Reliability	Why Selected (Why alternatives were not?)
Team Composition Assessment	Team	1	Which of the following people do you consider to be members of your team? [List of all practice members]: Member selects “Yes, always”, “Yes, sometimes”, “No”	NEW	Recognizing that individual members sometimes have different conceptions of their team membership boundaries, we aimed to clarify differences in administratively-defined team membership and individual reports of team composition, and consider these differences when interpreting the teamwork measures.
Team Processes / Relational Coordination	Team	7	Do people on your team communicate with you in a timely way about patient care? When there is a problem with patient care, do people on your team blame others or work with you to solve the problem?	0.80	Adapted: Use a team-based referent vs. a focal workgroup (external) ⁷¹ . We chose the RC over other measures of teamwork because more extensive validation and reliability information exists for RC compared to other teamwork measures such as the new AHRQ TeamSTEPPS measures ^{71, 94} .
Team Participation	Team	7	
 • I frequently contribute information • I frequently interpret information • I can comfortably disagree with other • I usually propose alternatives 	0.90	Among teamwork measures assessed in a recent systematic review, is one of three instruments that satisfied standard psychometric criteria and associated with non self-reported outcomes. Staff participation and engagement is also central to patient activation and engagement. ⁷²
Baldridge Award Adapted – Patient Centeredness	Practice	5	The practice does a good job of assessing current patient needs and expectations; staff promptly resolve patient complaints; patients'	0.86 (2004)	Used in previous research and found to be positively associated with changes to improve chronic illness care ([name],

PRINCIPAL INVESTIGATOR (LAST, FIRST, MIDDLE): [name]

Appendix III. Primary Care Teamwork, Relational Coordination, Leadership, and Culture Survey

(Number of questions= 40 excluding the team composition question)

Measure	Level	Item Count	Example Content	Internal Consistency Reliability	Why Selected (Why alternatives were not?)
			complaints are studied to identify patterns and prevent the same problems from recurring; the organization uses data from patients to improve services; and the organization uses data on customer expectations and/or satisfaction/experiences when designing new services.		2004). ⁷⁴
Leadership Facilitation (Organizational Readiness for Change Assessment-leadership behavior and change culture subscales)	Practice	7	Leadership and management in your practice... ...Reward clinical innovation and creativity to improve patient care ...Solicit opinions of clinical staff regarding decisions about patient care ...Seek ways to improve patient education and increase patient participation in treatment. ...Make sure that we have the time and space necessary to discuss changes to improve care ...Strongly support practice change efforts ...Promote an environment that is an enjoyable place to work ...Create an environment where things can be accomplished	0.94	We selected the ORCA measure of leadership because it is more specific to the changes related to PA&E initiatives while the AHRQ measure is more general.
Group Practice Organizational Culture	Practice	8	Innovation and Risk-taking in our practice 1. Successful innovations are highly publicized 2. Risk taking is encouraged 3. We consider ourselves to be the testing ground for new approaches to engage patients in their care	.80	Consideration was also given to the Competing Values measure of culture but being an ipsative scale it is more difficult for respondents to complete. We therefore decided to use the more straightforward measures developed and validated by

PRINCIPAL INVESTIGATOR (LAST, FIRST, MIDDLE): [name]

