We will assess culture at the practice level using two domains of the Group Practice Organizational Culture instrument⁷⁵, which focus on measuring the group and entrepreneurial culture orientations of teams. We posit that teams with more group and entrepreneurial oriented cultures will be associated with greater patient activation and engagement initiatives, patients that are more activated, and patients that will experience better outcomes of care. (see Appendix III)

Leadership Facilitation

We will use a seven-item subscale of the Organizational Readiness for Change (ORCA) to measure the extent to which team members believe that leadership and management supports them in their work to improve care for patients. It has an internal consistency reliability of 0.94 and has been used in previous studies assessing leadership facilitation of team and practice redesign⁷⁶⁻⁷⁸. (See Appendix III)

Feedback and Site Visits

We will work closely with the practice leaders and patient advisory groups in designing and developing feedback reports for the primary care teams. Some approaches which will be considered include^{65, 66}: 1) whether results are presented in a blinded or unblinded fashion, 2) how the information is delivered to the team, 3) facilitation and guidance for teams as they discuss their results, and 4) a system for disseminating best practices among teams within a practice site. We posit that practices with high teamwork assessments at baseline will be much more likely to undertake process improvements after receiving feedback on PROs and teamwork compared to practices with low teamwork assessments at baseline.

PRINCIPAL INVESTIGATOR (LAST, FIRST, MIDDLE): [name]

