With respect to the site visits and staff surveys performed at the 16 ACO practices, the information collected through the survey and in-depth interviews with physicians and other ACO executives pertains to each organization's professional activities only and does not pertain to any personal matters. The collection of these survey data do not pose any physical, financial, or legal risks to the ACO practice team members.

Adequacy of Protection Against Risks

Recruitment and Informed Consent

Informed consent will be obtained from all selected patients before completion of the survey. A written consent letter will be included with the mailed surveys and phone consent will be specifically obtained at the beginning of each follow-up CATI interview.

PRINCIPAL INVESTIGATOR (LAST, FIRST, MIDDLE): [name]

Informed consent will also be obtained from the team members surveyed during administration by UC Berkeley investigators.

Protections Against Risk

To minimize the risk of loss of confidentiality, all information with the potential to identify study participants will remain housed at Advocate Health and Health Care Partners, respectively, only accessible to Advocate Health and HealthCare Partners staff.

Potential Benefits of the Proposed Research to Human Subjects and Others

Patients may benefit from the feedback of the time one findings which could enable some of the practice sites to make changes which directly benefit some patients subsequent to time 2. Furthermore, the knowledge gained from this study at the participating ACOs could potentially benefit all enrolled patients. As large scale delivery systems begin to form and as the electronic health record becomes more prevalent, it becomes more possible for organizations to work with their patient populations to improve process and outcomes of care. The instruments from our study can be made available to other delivery systems to conduct such research in addition to what we learn about the role of PA&E in the research process.

Importance of the Knowledge to be Gained

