Appendix III. Primary Care Teamwork, Relational Coordination, Leadership, and Culture Survey
 (Number of questions= 40 excluding the team composition question)

Measure	Level	Item Count	Example Content	Internal Consistency Reliability	Why Selected (Why alternatives were not?)
			
4. We are given time to generate new ideas and innovations Group Solidarity in our practice
 
1. We have a strong sense of belonging to the practice
 
2. It would be hard for me to leave my colleagues at this practice
 
3. Team members openly share their patient care challenges and failures with each other
 
4. There is a well-defined pecking order among team members
		Kralewski ⁷⁵
Demographics	Individual	6	Age, sex, race/ethnicity, occupation, years working at practice, work hours/week.		

PRINCIPAL INVESTIGATOR (LAST, FIRST, MIDDLE): [name]

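### Two of the five patient-centeredness items in the staff survey refer to the organization, not the practice; this ambiguous wording may attenuate a practice-level score

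*Combined protocol and SAP*

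**What the plan says.** Appendix III lists the adapted Baldridge scale with Level = Practice, five items and a reliability of 0.86. All five items appear. The first is "The practice does a good job of assessing current patient needs and expectations". The second speaks of staff and the third, on studying complaints, names no unit. The last two read "the organization uses data from patients to improve services; and the organization uses data on customer expectations" and continue to the design of new services.

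The other two practice-level scales in that appendix fix their unit. The leadership items share a lead-in naming the respondent's practice, and both culture domains are headed as being about our practice. The body text agrees: "We will assess culture at the practice level". For relational coordination, the appendix records that the referent was deliberately changed to the team.

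The Team Effectiveness section includes the Baldridge scale, and perceived team effectiveness is one of the four teamwork instruments. Aim 5 enters teamwork as a predictor of patient activation and engagement (PA&E) activity, through an overall composite and through subscales. Teamwork results are also fed back to practices (Table 3).

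**The concern.** A practice-level score should be built from items that respondents answer about their practice. Here one item names the practice and two name a unit that could be the practice or its parent. The document itself uses the word both ways:

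- **For the ACOs:** the section on reproducibility and transparency uses *organizations* for the two participating systems, as does the statement of potential benefits under the Dartmouth human-subjects section.
- **For a practice:** the sample feedback report in Appendix IV compares one practice with other practices but heads its column Your Organization, including in the table covering the same five patient-centeredness topics.

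If staff answer for the ACO, the two items measure something common to all eight practices of that ACO. They add respondent noise and perhaps a difference between ACOs, but nothing that separates practices within one. The association between teamwork and PA&E activity in Aim 5 would then be weakened, and practices would receive a score that partly describes their parent body. With only 16 practices there is little room for such a loss.

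**Working it through.** **The plan's own count.** Appendix III states "Number of questions= 40 excluding the team composition question". Its rows give 7 + 7 + 5 + 7 + 8 + 6 (demographics) = 40, which agrees. The practice-level items are 5 + 7 + 8 = 20, and two of them name the organization.

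**Practice-level reliability.** Assumed inputs, not in the documents: staff intraclass correlation (ICC) 0.05 to 0.20 and 20 to 40 respondents per practice (n). Let w be the share of their practice signal that the two items keep (1 if read as the practice, 0 if all answer for the ACO). The score's practice signal is then (3 + 2w)/5 of its full size, and its practice variance is s = ICC × ((3 + 2w)/5)². Respondent variance is held fixed and no ACO component is added.

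Reliability = s / (s + (1 − ICC)/n). The correlation with PA&E scales with the square root of reliability. At ICC 0.10 and n = 20, (1 − ICC)/n = 0.045:

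- w = 1: 0.100/0.145 = 0.69; correlation ratio 1.00.
- w = 0.5: s = 0.64 × 0.10 = 0.064; 0.064/0.109 = 0.59; ratio √(0.587/0.690) = 0.92.
- w = 0: s = 0.36 × 0.10 = 0.036; 0.036/0.081 = 0.44; ratio √(0.444/0.690) = 0.80.

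Range at w = 0:

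- ICC 0.05, n = 20: 0.050/0.0975 = 0.513 falls to 0.018/0.0655 = 0.275; ratio 0.73.
- ICC 0.20, n = 40: 0.200/0.220 = 0.909 falls to 0.072/0.092 = 0.783; ratio 0.93.

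**Cross-check from the stated reliability.** This uses the stated 0.86 and an assumed one-factor model with equal loadings. The mean inter-item correlation is 0.86/(5 − 4 × 0.86) = 0.55. Multiplying the loadings of the two items by w gives:

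| w | alpha | correlation with construct, relative to w = 1 |
|---|---|---|
| 1 | 0.86 | 1.00 |
| 0.75 | 0.80 | 0.97 |
| 0.5 | 0.72 | 0.93 |
| 0.25 | 0.63 | 0.88 |
| 0 | 0.50 | 0.83 |

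Both routes run from no loss to a moderate loss. The deciding quantity, w, cannot be learned from the documents.

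**The case against.** The strongest reply is that nothing shows staff will misread the items. Appendix IV uses *organization* for a practice on these same topics. The human-subjects wording, "physicians and other ACO executives pertains to each organization's professional activities only", comes in a sentence about site visits and staff surveys at the 16 practices, so it settles nothing. This stands against any claim that the items ask about the wrong unit. It does not remove the ambiguity, because the document also uses the word for the ACOs.

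A second reply is that the column is headed Example Content, the appendix is optional, and patient advisory groups will help finalize instruments. The fielded wording may differ or carry a lead-in naming the practice. That is fair, and is a reason to settle the wording now.

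Third, psychometric analysis is planned at each wave. It cannot recover answers already given about another unit, and internal consistency can stay high if staff answer consistently for the ACO.

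Fourth, Aim 5 is exploratory, patient-centeredness is not among its named example subscales, and drawing four high and four low practices from each ACO balances ACO differences across that contrast. All of this limits the consequence. The balance does not restore lost practice signal, and the scale can still enter through team effectiveness and the composite.

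A reader might also infer that the culture score is damaged by the Group Solidarity item "There is a well-defined pecking order among team members", which runs against its neighbours and has no reverse-scoring mark. The documents do not support that. No scoring key is given for any scale, and nothing says the item will be summed unreversed. Assuming equal loadings, leaving it unreversed would take the four-item alpha to 0.00, or the eight-item alpha from 0.80 to about 0.62. The planned analysis should expose this, and it can be corrected at scoring.

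**Conclusion.** The point holds as a minor one: two of five items in a scale labelled practice-level have an ambiguous referent, and the score may be attenuated to the extent that staff answer for the ACO. The effect on correlations with PA&E activity runs from none to about 0.80 of their size at an ICC of 0.10 and 20 respondents (0.73 to 0.93 across the assumed ranges). The lower figures require every respondent to answer for the ACO. ICC, respondent numbers and loadings are assumptions.

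The stronger reading, that the practice scores are in fact diluted, does not follow, because the documents do not show how staff will read the word. The scoring direction of the pecking-order item is a documentation note only.

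**What to change.** Before wave 1 is fielded, replace *the organization* with *this practice* in the two Baldridge items, and keep that wording at both waves so that changes in team factors are not confounded with a change in wording. The cost is an edit to two items in a scale that is already adapted, and slightly less comparability with its 2004 version. While editing Appendix III, the sponsor could also record the scoring direction of the pecking-order item. That needs no change to the fielded survey.

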Appendix III. Primary Care Teamwork, Relational Coordination, Leadership, and Culture Survey
 (Number of questions= 40 excluding the team composition question)

Measure	Level	Item Count	Example Content	Internal Consistency Reliability	Why Selected (Why alternatives were not?)
			
4. We are given time to generate new ideas and innovations Group Solidarity in our practice
 
1. We have a strong sense of belonging to the practice
 
2. It would be hard for me to leave my colleagues at this practice
 
3. Team members openly share their patient care challenges and failures with each other
 
4. There is a well-defined pecking order among team members
		Kralewski ⁷⁵
Demographics	Individual	6	Age, sex, race/ethnicity, occupation, years working at practice, work hours/week.		

PRINCIPAL INVESTIGATOR (LAST, FIRST, MIDDLE): [name]

Appendix IV. NATIONAL STUDY OF PHYSICIAN ORGANIZATIONS III—FEEDBACK REPORT EXAMPLE

Comparison of <>Your Practice<> with all other physician practices surveyed

Note: The “your organization” column reflects your self-reported survey responses

Care Management Processes Indices Score*						
	Your Organization	Mean Scores				
		All Practices	1-7 physicians	8-19 physicians	20-99 physicians	100+ physicians
Practice provides patient educators (0-4)		1.5	1.3	1.5	1.9	2.3
Practice provides performance feedback to physicians (0-4)		1.1	1.0	1.3	1.4	2.0
Practice uses nurse care managers for chronic disease (0-4)		0.6	0.5	0.6	0.9	1.6
Practice sends patients reminders for preventive or follow-up care (0-4)		1.3	1.3	1.3	1.4	1.7
Provider receives clinical practice guideline reminders at point of care (0-4)		1.3	1.3	1.3	1.4	1.7
Practice maintains electronic registry of patients with chronic condition (0-4)		1.1	0.9	1.2	1.4	1.9
Overall Care Management Processes Index (0-24)		6.9	6.1	7.1	8.3	11.1
Care Management Process Percent Score**		28.9%	26.0%	30.2%	34.7%	46.4%

The Care Management Processes Indices are based on a “yes” response to a series of six questions regarding use of the specified processes for patients with asthma, congestive heart failure, depression, or diabetes. It is only possible to receive all points if your practice treats all conditions.

**The “Care Management Process Percent Score” takes into account that a practice may not treat all conditions and reflects the points received out of points possible regarding conditions treated at your practice,

Enhanced Access Index Score						
	Your Organization	Percentage/ Mean Scores				
		All Practices	1-7 physicians	8-19 physicians	20-99 physicians	100+ physicians
Majority of physicians communicate with patients via e-mail		18.4%	19.1%	13.2%	13.1%	31.3%
Practice allows patients to view medical record online		24.3%	18.6%	27.0%	36.5%	56.3%

PRINCIPAL INVESTIGATOR (LAST, FIRST, MIDDLE): [name]

Physicians use "advanced access" scheduling		21.4%	16.3%	27.0%	32.1%	43.8%
Practice is open extended hours or on weekends		59.3%	53.3%	61.6%	78.1%	82.5%
Practice uses group visits		16.5%	11.2%	19.5%	29.2%	42.5%
Overall Enhanced Access Index (0-5)		1.4	1.2	1.5	1.9	2.6

Care Coordination/Integration Index

	Your Organization	Percentage/ Mean Scores				
		All Practices	1-7 physicians	8-19 physicians	20-99 physicians	100+ physicians
Majority of physicians use the EMR for progress notes		64.2%	55.0%	75.5%	87.6%	95.0%
Electronic access to view emergency department records and hospital discharge summaries		75.4%	71.1%	88.1%	80.3%	86.3%
Majority of physicians send prescriptions directly to pharmacies electronically		81.5%	76.2%	91.2%	92.0%	97.5%
Overall Care Coordination/ Integration Index (0-3)		2.2	2.0	2.5	2.6	2.8

Patient-Centered Care Index

	Your Organization	Percentage/ Mean Scores				
		All Practices	1-7 physicians	8-19 physicians	20-99 physicians	100+ physicians
Assess patient needs and expectations		48.7%	54.4%	45.3%	29.9%	30.0%
Promptly resolve patients' complaints		47.2%	52.3%	39.0%	35.8%	31.3%
Complaints studied to identify patterns and prevent recurrence		35.0%	38.4%	28.9%	27.0%	37.5%
Data from patients used to improve care		30.1%	30.2%	28.3%	27.0%	37.5%
Data from patients used to develop new services		17.4%	18.1%	14.5%	16.1%	18.8%
Overall Patient-Centered Care Index (0-5)		1.8	1.9	1.6	1.3	1.5
